6.5.4 Baseline Visit

The Baseline visit occurs 3 weeks (+3 days) after the screening visit. Eligibility must be confirmed prior to randomization. At the Baseline visit, the following procedures and assessments are to be performed, preferably in the order shown below:

- Ask the subject to complete the WI-VAS, ESS, and sPGA questionnaires
- Assess and record any changes in the subject's concomitant medications

- Assess and record any changes in the subject's medical history
 - Female subjects should be queried regarding history of, or current, breast masses or abnormal discharge, and history of mammography (if applicable), and history of abnormal vaginal bleeding or discharge
- Assess AEs and record SAEs caused by protocol-mandated interventions
- Obtain vital signs
- Perform a urine pregnancy test for females of childbearing potential and confirm the subject has a negative urine pregnancy test result prior to randomization (with positive or equivocal results confirmed by a serum pregnancy test)
- Confirm subject's eligibility based on the inclusion/exclusion criteria (to include review of eDiary compliance for eligibility)
- Randomize subject in IWRS if eligibility confirmed
- Perform targeted physical examination, including weight
- Dispense 1 bottle of study drug; subjects will take loading dose of 3 tablets while on site
- Assess and record any post-dose AEs and SAEs
- Confirm next scheduled visit

6.5.5 *Week 1 Telephone Contact Visit*

The Week 1 visit is a telephone visit that occurs 7 days (\pm 3 days) after the Baseline visit. At the Week 1 visit, the following procedures and assessments are to be performed:

- Assess and record any changes in the subject's concomitant medications
- Assess and record any AEs and SAEs
- Review eDiary for compliance, re-train subject as needed
- Review study drug compliance with re-training as required
- Confirm next scheduled visit

6.5.6 *Week 2 Visit*

The Week 2 visit occurs 14 days (-3/+1 days) after the Baseline visit. At the Week 2 visit, the following procedures and assessments are to be performed:

- Ask the subject to complete the WI-VAS, ESS, sPGA, and PGIC questionnaires

- Assess and record any changes in the subject's concomitant medications
- Female subjects should be queried for presence of new breast masses or abnormal discharge, and abnormal vaginal bleeding or discharge
- Obtain vital signs
- Assess and record any AEs and SAEs
- Review eDiary for compliance, re-train subject as needed

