- Review study drug compliance with re-training as required
- Collect returned study drug
- Utilize IWRS to assign 1 new bottle of study drug
- Confirm next scheduled visit date

6.5.7 *Week 4 Visit*

The Week 4 visit occurs 28 days (\pm 3 days) after the Baseline visit. At the Week 4 visit, the following procedures and assessments are to be performed:

- Ask the subject to complete the WI-VAS, ESS, sPGA, and PGIC questionnaires
- Assess and record any changes in the subject's concomitant medications
- Female subjects should be queried for presence of new breast masses or abnormal discharge, and abnormal vaginal bleeding or discharge
- Obtain ECG
- Obtain vital signs
- Perform a urine pregnancy test for females of childbearing potential (with positive or equivocal results confirmed by a serum pregnancy test)
- Draw blood for clinical laboratory tests
 - Hematology
 - Chemistry
- Perform targeted physical examination, including weight
- Assess and record any AEs and SAEs
- Collect returned study drug
- Utilize IWRS to assign 1 new bottle of study drug

- Review eDiary for compliance, re-train subject as needed
- Review study drug compliance with re-training as required
- Confirm next scheduled visit date

6.5.8 *Week 6 Visit*

The Week 6 visit occurs 42 days (\pm 3 days) after the Baseline visit. At the Week 6 visit, the following procedures and assessments are to be performed:

- Ask the subject to complete the WI-VAS, ESS, sPGA, and PGIC questionnaires
- Assess and record any changes in the subject's concomitant medications
- Female subjects should be queried for presence of new breast masses or abnormal discharge, and abnormal vaginal bleeding or discharge
- Obtain vital signs
- Perform targeted physical examination, including weight
- Assess and record any AEs and SAEs
- Collect returned study drug
- Utilize IWRS to assign 2 new bottles of study drug
- Review eDiary for compliance, re-train subject as needed
- Review study drug compliance with re-training as required
- Confirm next scheduled visit date

6.5.9 *Week 8 Telephone Contact Visit*

The Week 8 visit is a telephone visit that occurs 56 days (\pm 3 days) after the Baseline visit. At the Week 8 visit, the following procedures and assessments are to be performed:

- Assess and record any changes in the subject's concomitant medications
- Assess and record any AEs and SAEs
- Review eDiary for compliance, re-train subject as needed
- Review study drug compliance with re-training as required

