2.3.7.2 Other Safety Endpoints

- Vital signs:
 - Systolic Blood Pressure, Diastolic Blood Pressure, Heart Rate, Respiration Rate, Height, Weight, Temperature and presence of a clinically significant abnormal values.
- 12-Lead Electrocardiogram:
 - RR, PR, QRS, QT, HR, QTcB, QTcF, and the ECG interpretation. A central read cardiologist assessment of normal vs abnormal will be available as well as an investigator assessment of clinically significant vs not clinically significant.
- Physical examination abnormalities identified as preexisting before treatment will be recorded as medical history. Abnormalities identified after treatment will be recorded as adverse events.

- Laboratory samples will include:
 - Hematology, Chemistry, Immunochemistry and Urine Pregnancy.

2.3.8 *Pharmacokinetic Measurements*

There will be one PK sample at the Week 10 visit. The plasma concentrations of serlopitant and metabolites M1/M1a, M2/M2a and M3 will be determined.

2.4 **Study Day and Visit Windows**

Summary tables will report data based upon the protocol scheduled time points (Baseline, Weeks 2, 4, 6, 10 and Follow-up). Assessment will be assigned to these time points based upon the study day they are performed on. The derivation of study day depends upon whether the event occurred prior to or after treatment. This results in the first day of treatment being on day 1 and the day prior to the first day of treatment being day -1. For events that occur prior to the first day of treatment the following definition is used,

$$\text{Study day} = \text{date of assessment} - \text{date of first treatment}.$$

For events that occur on or after the first day of treatment, a plus one is added,

$$\text{Study day} = \text{date of assessment} - \text{date of first treatment} + 1.$$

The analysis windows used to report non-daily endpoints are outlined in [Table 3](#). If more than one assessment is available within the range, the assessment closest to the target day is reported for the analyses window. If two observations exist with the same distance to the target day, the first observation is used.

Table 3 Analysis Windows

Visit	Range	Target Day
Screening	< Day - 7	First
Baseline	Day -7 to Day 1	Day 1
Week 2	Day 2 to Day 21	Day 15
Week 4	Day 22 to Day 35	Day 29
Week 6	Day 36 to Day 57	Day 43
Week 10	> Day 57	Day 71

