In addition to the analysis windows, data will be summarized at Follow-Up. The Follow-Up assessment will be the last assessment available that is at least seven days after the end of treatment. Should no post treatment assessments be available, the subject will not have a follow-up assessment. The baseline of an endpoint (see [Section 3.2](#)) may not always occur at the baseline visit.

The eDiary WI-NRS assessments will be summarized at Baseline, Week 2, 4, 6, 10, and Follow-up. The seven days leading up to the time point (see [Table 4](#) range), will be used to create the summary measures unless the subject does not have at least seven results. In this case, as many observations available within the complete data range will be used and additional data from the extended range (see [Table 4](#)) will be used until seven data points are achieved, or the end of the extended range is reached. An example of this algorithm can be found in [Section 3.4.1](#)

Table 4 Daily Windows

Visit	Range (complete data)	Extended Range
Baseline ^a	Day -7 to -1 or Day -6 to -1, Day 1	Day -11 to -8 or Day -10 to -7
Week 2	Day 8 to Day 14	Day 15 to Day 18
Week 4	Day 22 to Day 28	Day 29 to Day 32
Week 6	Day 36 to Day 42	Day 43 to Day 46
Week 8	Day 47 to Day 53	Day 54 to Day 57
Week 10	Day 64 to Day 70	Day 60 to Day 63

^a If the diary was completed prior to dosing on Day 1 then the baseline range includes the day of dosing (Day 1) otherwise the baseline range does not include Day 1.

An additional ‘Follow-Up’ timepoint will also be created. This timepoint includes the last 7 post treatment observations that are at least 7 days after the end of treatment.

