3.4 Analysis of Efficacy Endpoints

3.4.1 Calculation Examples for Daily Measures

Below are examples of how the eDiary WI-NRS weekly results will be calculated based upon windows outlined in [Table 4](#) and rules outlined in [Section 2.4](#).

1. Example 1 (complete data)
 - a. The subject has results for all seven days leading up to the visit (e.g. $x_8, x_9, x_{10}, x_{11}, x_{12}, x_{13}, x_{14}$).
 - b. The average for Week 2 is $(x_8 + x_9 + x_{10} + x_{11} + x_{12} + x_{13} + x_{14})/7$.
2. Example 2 (incomplete data, completed in the extended range)
 - a. The subject has results for less than seven days in the original range (e.g. $x_{22}, x_{24}, x_{25}, x_{27}, x_{28}$) but have enough in the extended range to reach seven results overall (e.g. x_{29}, x_{31}). In this example the subject is missing diary data on days 23, 26, and 30.
 - b. The average for Week 4 is $(x_{22} + x_{24} + x_{25} + x_{27} + x_{28} + x_{29} + x_{31})/7$.
3. Example 3 (incomplete data)

- a. The subject has results for less than seven days in the original range (e.g. x_{39} , x_{40} , x_{42}) and does not have enough in the extended range to reach seven results overall (e.g. x_{44} , x_{46}). In this example the subject is missing diary data on days 36, 37, 38, 41, 43 and 45.
 - The average for Week 6 is $(x_{39}+x_{40}+x_{42}+x_{44}+x_{46})/5$.
4. Example 4 (no data)
 - a. The subject does not complete the diary from day 60 onwards.
 - b. The average for Week 10 is missing and the missing data rules ([Section 2.7](#)) are used.

3.4.2 *WI-NRS*

The WI-NRS endpoints (result, change from baseline, 3-point and 4-point responders) will be summarized at the primary time point (Week 10) as well as at Weeks 2, 4, 6, 8 and Follow-up. The summary measures will include 95% Wald confidence intervals for the treatment difference and a p-value for the treatment difference (for the change from baseline and responder rate measures). The baseline WI-NRS will also be summarized, but no confidence interval will be produced. A graph of the mean WI-NRS results and mean change from baseline results and the 4-point responder rate (baseline included with a rate of zero) by timepoint and treatment will be produced.

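### The Week 8 diary window in SAP Table 4 (Day 47–53) is three days earlier than the SAP's own rule and the other four post-baseline rows imply (Day 50–56), and no reason is given

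*SAP*

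**What the plan says.** SAP 2.4 (Study Day and Visit Windows) sets the rule for the diary endpoint: "The seven days leading up to the time point" are averaged, with the ranges in Table 4. SAP 3.4.1, Example 1, restates it for Week 2: "The subject has results for all seven days leading up to the visit", which there are Days 8 to 14.

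The first treatment day is Day 1: "For events that occur on or after the first day of treatment, a plus one is added". A visit 56 days after Baseline therefore falls on Day 57. The protocol places the Week 8 contact there (section 6.5.9): "The Week 8 visit is a telephone visit that occurs 56 days", ± 3 days.

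Table 4 gives these complete-data ranges: Week 2 Day 8–14, Week 4 Day 22–28, Week 6 Day 36–42, Week 8 "Day 47 to Day 53", and Week 10 Day 64–70. The Week 8 extended range is Day 54–57. The table's only footnote concerns Baseline, and the worked examples in SAP 3.4.1 cover Weeks 2, 4, 6 and 10 but not Week 8.

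The sentence in SAP 2.4 that lists the diary time points leaves Week 8 out, although Table 4 and SAP 2.3, 2.5.2 and 3.4.2 all include it.

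**The concern.** One row of a five-row table departs from the rule it is meant to implement, and nothing says that this is intended. It looks like a slip in a specification that programmers will follow literally.

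Two things depend on it:

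- **Week 8 key secondary endpoints.** The 4-point rate, the 3-point rate and the change from baseline at Week 8 are all tested. As printed they describe a week centred three days earlier than the rule gives, so Week 8 is not aligned with its nominal time as the other weeks are. The plots by time point in SAP 3.4.2 inherit this.
- **Imputed Week 10 values.** Under SAP 2.7, a subject with no Week 10 value receives the last known value plus the treatment group's mean change from then on, and the Week 8 to Week 10 change is one of those increments. The Week 8 window therefore affects who has a Week 8 value to start from, and both terms of the sum. The multiple-imputation sensitivity analysis in SAP 3.4.2 uses the same windows.

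**Working it through.** **Inputs.** The averaging rule and study-day convention come from SAP 2.4, the ranges from SAP Table 4, and the visit days and windows from protocol 6.5.6 to 6.5.10. For example: "The Week 2 visit occurs 14 days (-3/+1 days) after the Baseline visit"; "The Week 4 visit occurs 28 days" (± 3 days); "The Week 6 visit occurs 42 days" (± 3 days). Week 8 is also ± 3 days, and Week 10 is + 3 days only.

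**Step 1: apply the rule.** A visit 7w days after Baseline falls on Day 7w + 1. The seven days before it are Day 7w − 6 to Day 7w.

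| Week | Nominal day | Rule gives | Table 4 prints | Match |
|---|---|---|---|---|
| 2 | 15 | 8–14 | 8–14 | yes |
| 4 | 29 | 22–28 | 22–28 | yes |
| 6 | 43 | 36–42 | 36–42 | yes |
| 8 | 57 | 50–56 | 47–53 | no, 3 days early |
| 10 | 71 | 64–70 | 64–70 | yes |

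The rule reproduces four rows exactly. The Week 8 row ends four days before its nominal day; every other row ends one day before.

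**Step 2: test the earliest permitted contact as an explanation.** The earliest visit days are 15 − 3 = 12, 29 − 3 = 26, 43 − 3 = 40, 57 − 3 = 54 and 71 − 0 = 71. The seven days before these are 5–11, 19–25, 33–39, 47–53 and 64–70. This fits Weeks 8 and 10 but not Weeks 2, 4 and 6. Week 10 fits both readings because its visit window has no early side.

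**Step 3: size of the displacement.** Day 47–53 and Day 50–56 share Days 50–53, or 4 of 7. With a complete diary, Days 47–49 are used and Days 54–56 are not. With 1, 2 or 3 gaps in Day 47–53, the extended range can bring back Day 54, 54–55 or 54–56. Window midpoints as printed are 11, 25, 39, 50 and 67, so the steps are 14, 14, 11 and 17 days. With Day 50–56 the Week 8 midpoint is 53 and every step is 14.

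**Step 4: effect on imputed Week 10 values.** For a subject last seen at Week 8:

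imputed W10 = own W8 + (group W10 − group W8).

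Moving the Week 8 window changes this by (own W8 shift − group W8 shift), which is zero only if the two shifts are equal. Separately, a diary ending on Day 47–49 yields a Week 8 value as printed but none under Day 50–56, so the imputation would then start from an earlier week.

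**Step 5: indicative size for the Week 8 treatment difference.** Protocol 1.3.3 reports differences of −0.9, −1.0 and −1.7 at Weeks 2, 4 and 8 in the earlier prurigo nodularis study. The slopes are (1.0 − 0.9)/2 = 0.05 and (1.7 − 1.0)/4 = 0.175 points per week. Over three days (× 3/7) that is 0.02 to 0.075 points, and 0.075/1.7 = 4.4%. This is average VAS in another population. It illustrates scale, is not a bound, and does not translate into responder rates.

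**The case against.** The strongest reply is that the row may be deliberate. Joining each complete range to its extended range gives blocks of Days 8–18, 22–32, 36–46, 47–57 and 60–70. Each is 11 days long, none overlap, and each lies inside a single range of SAP Table 3. A Week 8 block of Days 50–60 would cross Table 3's boundary after Day 57 and share Day 60 with the Week 10 extended range. Day 47 is also the first day after the Week 6 extension.

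This is a coherent account, but it is not written anywhere. Table 3 governs non-daily endpoints only. Starting each week straight after the previous extension would put Week 4 at Day 19 and Week 6 at Day 33, which Table 4 does not do. Day 50–56 itself overlaps no other window and ends before Day 57, so the difficulty lies in the extension and does not require moving the complete range.

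Some of the reply stands:

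- Day 50–56 is also an inference, since Table 3 has no Week 8 target day.
- The misfit is in the complete range. The printed extension follows directly and lasts four days, as in Weeks 2, 4 and 6; it is Week 10 that extends backward.
- The printed row is unambiguous, can be programmed as it is, and is the same in both arms.
- SAP 2.5 makes the secondary p-values descriptive.
- The route to the primary endpoint is narrow: it needs no diary entry on Days 60–70 and no intercurrent event.

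**Conclusion.** The inconsistency holds. The Week 8 row does not follow the SAP's stated rule, four of the five post-baseline rows do, and no reason is given. The displacement is three days, affecting three of the seven days in a complete diary.

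Confidence in the inconsistency is high. That Day 50–56 was intended is inferred from the rule, the other rows and the protocol's Week 8 contact on Day 57.

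The Week 8 key secondary results are directly affected, probably by little. The observed Week 10 primary endpoint is untouched. For imputed Week 10 values, neither the size nor the direction of the effect can be derived from the documents. This is a low-severity item to correct or justify. It is worth settling now because changing the window after unblinding would be a post-hoc change to tested endpoints.

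**What to change.** Before unblinding, do one of the following in SAP 2.4:

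- Change the Week 8 row of Table 4 to Day 50–56 with extended range Day 57–59. This extension uses no day belonging to another week. It is one day shorter than in the other rows, so a subject with four gaps could not reach seven values at Week 8. The four-day alternatives each share a day: Day 57–60 shares Day 60 with the Week 10 extension, and Day 46–49 shares Day 46 with the Week 6 extension. The choice should be stated.
- If Day 47–53 was intended, keep it and give the reason in one sentence.

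Also add Week 8 to the SAP 2.4 sentence listing the diary time points, and check the opening sentence of SAP 2.4, whose list of summary time points omits it too.

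The cost is one table row or one sentence, plus an editorial correction. Data collection and sites are not affected.

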2.5 Statistical Assessment of the Study Objectives

The efficacy endpoints will be summarized within the FAP using descriptive statistics by time point and treatment. For the primary and key secondary endpoints, these statistics will include 95% confidence intervals for the treatment difference. Testing will also be used for the primary and key secondary endpoints. No multiplicity adjustment will be used, and the p-values reported for the key secondary endpoints will be descriptive in nature.

2.5.1 Primary Analysis

The difference in the primary efficacy outcome measure (WI-NRS 4-point responder rate at Week 10) between treatment groups will be summarized by treatment group. The difference in responder rates between treatment arms will be tested using a Cochran-Mantel-Haenszel (CMH) test controlling for the ‘as randomized’ stratification factors. Conceptually, the hypotheses being tested are:

$$H_0: \pi_p \geq \pi_s \qquad H_a: \pi_p < \pi_s$$

where π_p is the placebo responder rate at Week 10 and π_s is the similar measure for serlopitant.

The primary endpoint will utilize the analysis windows outlined in [Section 2.4](#), the intercurrent rules outlined in [Section 2.6](#), and the missing data rules outlined in [Section 2.7](#).

2.5.2 *Secondary Analyses*

Secondary endpoints will be summarized with descriptive statistics by time point and treatment. These summary measures will include baseline, result at the time point, and change from baseline as is appropriate for the endpoint. Missing data imputation will be limited to the WI-NRS endpoint.

The differences between treatment groups for the WI-NRS 4-point at Weeks 2, 4, 6, and 8, and 3-point responder rates at Weeks 2, 4, 6, 8, and 10 will be tested using the CMH test identical to the one used for the primary endpoint.

The change from baseline to Weeks 2, 4, 6, 8, and 10 for the WI-NRS will be tested using an analysis of variance (ANOVA) model with treatment group and stratification factor as fixed effects. A separate model/test will be performed at each time-point. [REDACTED]

CCI

[REDACTED]

The change in WI-VAS to Weeks 2, 4, 6, and 10 will be tested using a similar ANOVA model.

2.6 **Intercurrent Event**

Intercurrent events include withdrawal from the study due to lack of efficacy or rescue therapy use for treatment of worsening pruritus. Rescue therapy will be identified by the site who indicate if medications were taken to treat worsening of pruritus.

Subjects who withdraw from the study early following stopping treatment due to an intercurrent event will have WI-NRS datapoints following the events set to the larger of baseline and the last WI-NRS value prior to the event. For rescue therapy this value will be imputed from the start of rescue therapy to 4 weeks after the end of this therapy. This approach will result in subjects being defined as non-responders following the intercurrent event.

[figure not shown]
The missing data rules outlined in [Section 2.7](#) will not be used for the results following an intercurrent event.

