8.8 Efficacy Analyses

All efficacy endpoints will be summarized within the FAP using descriptive statistics by time point and treatment.

8.8.1 *WI-NRS*

Subject record their WI-NRS measurements daily in an electronic diary. These daily measures are combined into weekly measures (Baseline, Weeks 2, 4, 6, 8, 10, Follow-up) by averaging the daily measurements. Change from baseline is the difference between baseline and the post baseline weeks. Missing data will be imputed as outlined in [Section 8.2](#). From this change from baseline the binary responder status (responder / non-responder) is created. A subject is a 4-point responder if their change from baseline is ≤ -4 (i.e. a decrease of at least 4). A 3-point responder is similarly defined. Subjects who withdraw from the study due to a lack of efficacy or require rescue therapy for treatment of worsening pruritus within four weeks prior to the timepoint will be defined as non-responders regardless of their change from baseline.

The daily WI-NRS endpoint (change from baseline in daily WI-NRS scores through Week 2) is the change between the baseline WI-NRS (same baseline as the weekly measures) and the daily measures over the first two weeks.

8.8.2 *Primary Efficacy*

The WI-NRS 4-point responder rate at Week 10 (primary endpoint) will be summarized by treatment group. The difference in responder rates between treatment arms will be tested using a CMH test controlling for the ‘as randomized’ stratification factors. Conceptually the hypotheses being tested are:

$$H_0: P_{Placebo} \geq P_{serlopitant} \quad H_a: P_{Placebo} < P_{serlopitant}$$

where $P_{Placebo}$ is the percent of placebo responders and $P_{serlopitant}$ is the similar percent for serlopitant.

Sensitivity analyses using other missing data rules will be performed.

8.8.3 *Secondary Efficacy and Exploratory*

Secondary endpoints will be summarized with descriptive statistics by time point and treatment. These summary measures will include baseline, result at the time point and change from baseline as is appropriate for the endpoint. Missing data imputation will be limited to the WI-NRS and WI-VAS endpoints.

The differences between treatment groups for the WI-NRS 4-point at Weeks 2, 4, 6, and 8, and 3-point responder rates at Weeks 2, 4, 6, 8, and 10 will be tested using the CMH test identical to the one used for the primary endpoint.

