The change from baseline to Weeks 2, 4, 6, 8, and 10 and Days 1–14 for the WI-NRS will be testing using an analysis of variance (ANOVA) model with treatment group and stratification factor as fixed effects. The change in WI-VAS to Weeks 2, 4, 6, and 10 will be tested using a similar ANOVA model.

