2.7 Handling of Missing Data

Summary statistics will generally be reported based upon observed data. Should a determination of treatment period (on treatment or pre-treatment) be required for adverse events or concomitant medication but the corresponding date is missing or partial, the event/medication will be considered on treatment unless the portions of the date that are available indicate this is not possible.

If a subject fails to complete their eDiary for a week or more, the WI-NRS endpoints, including the primary endpoint, may be missing. In this case, the WI-NRS change from baseline value will be imputed. The approach uses the subject's last week with data. From that point forward their trajectory will be imputed based upon the trajectory of their treatment group.

The imputation approach first determines the average change between analysis weeks (see [Table 4](#)) for each treatment group. The change between analysis weeks is the difference between results at adjacent analysis Weeks (e.g. results at Week 10 – results at Week 8). Any missing change from baseline results will be imputed by combining the last known value and the treatment group mean weekly differences from that point forward. CCI

This imputation algorithm is only used if the intercurrent events (see [Section 2.6](#)) did not occur.

For the responder endpoints, the same imputation will be performed and the responder status determined based upon the change from baseline.

Missing data imputation will only be used for the WI-NRS endpoints.

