The WI-NRS scores for days 1 to 14 will be plotted by averaging the available data across subjects within treatment group and study day. These results will be summarized in a table along with change from baseline, where baseline is defined in the identical manner used for the weekly measures. Daily WI-NRS results will be summarized in a table based upon availability of the data regardless of any intercurrent events.

The test used for the 3 and 4-point responder rates at Weeks 2, 4, 6, 8 and 10 is a CMH test controlling for the ‘as randomized’ stratification factors. The ‘as randomized’ stratification factors are based upon the stratification cell that the subject was randomized to. The differences between treatment groups for the change from baseline measure will be tested using an ANOVA model controlling for the stratification factors. A main effects model with an interaction term (treatment by stratification factors) and a Type II hypothesis will be used. The estimated treatment effect from this test will be a weighted average based upon the equation provided in [Section 2.5](#).

The WI-NRS 4-point responder rates at Week 10 will be summarized within the subgroups and separately by the post baseline factors outlined in [Section 2.8](#). Forest plots based upon the same groups will also be produced.

A missing data sensitivity analysis will be conducted using the multiple imputation method outlined in [Section 2.8](#). This analysis will include summary statistics by time points for the 4-point WI-NRS responder rate and the continuous WI-NRS measures as well as testing for the 4-point WI-NRS responder endpoint at Week 10. The following steps will be followed:

1. Using the daily eDiary data, the windows in Table 4 and the intercurrent rules outlined in Section 2.6 calculate the weekly WI-NRS values. Within this will be unknown values (i.e. no data within the Table 4 windows)
2. The missing WI-NRS values will be filled in using the MCMC method to generate at least 1000 datasets. [REDACTED] CCI [REDACTED]
[REDACTED]
[REDACTED]
[REDACTED]
3. From each dataset the responder status will be determined.
4. The resulting point estimates (Mantel Haenszel treatment effect and standard error) and the responder rate p-value from the data will be calculated using the SAS software procedure Freq.
5. These results will be combined with the SAS software procedure mianalyze.

3.4.3 *WI-VAS*

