The WI-VAS endpoint will be summarized with descriptive statistics at Baseline, Weeks 2, 4, 6, 10 and Follow-up. The summary measures will include 95% Wald confidence intervals of the treatment difference. In addition, a graph of the mean score by treatment and timepoint will be produced. The differences between treatment groups for the change from baseline measure will be tested using an ANOVA model similar to the WI-NRS endpoint.

3.4.4 *Exploratory Endpoints*

The ESS endpoint will be summarized at Baseline, Weeks 2, 4, 6, 10 and Follow-up. The total score and change from baseline in the total score will be summarized. The difference in average scores between treatment group will be summarized.

The sPGA endpoint will be summarized at Baseline, Weeks 2, 4, 6, 10 and Follow-up. The categorical result (e.g. Mild, Moderate, ...) will be summarized at each timepoint for each treatment group.

The PGIC will be summarized at Weeks 2, 4, 6, 10 and Follow-up. The categorical result will be summarized at each timepoint.

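### The WI-VAS change score is tested without baseline WI-VAS as a covariate; adding it costs one degree of freedom and probably brings a modest gain in precision

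*SAP*

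**What the plan says.** Protocol 8.8.3 tests change in WI-NRS with an "analysis of variance (ANOVA) model with treatment group and stratification factor as fixed effects" and gives WI-VAS a similar model. SAP 2.5.2 repeats this: "The change in WI-VAS to Weeks 2, 4, 6, and 10 will be tested using a similar ANOVA model". SAP 3.4.2 gives more detail for WI-NRS: "A main effects model with an interaction term (treatment by stratification factors) and a Type II hypothesis will be used". It adds that the estimated effect is a weighted average from an equation in Section 2.5. SAP 3.4.3 points WI-VAS back to that model: "The differences between treatment groups for the change from baseline measure will be tested using an ANOVA model similar to the WI-NRS endpoint". On the interval, it says only: "The summary measures will include 95% Wald confidence intervals of the treatment difference".

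The strata are age (under 50, or 50 and over) and weekly baseline WI-NRS (7 to under 8.5, or 8.5 to 10), per SAP 1.4. WI-VAS is completed on paper at the Baseline visit (protocol 6.5.4), and SAP 3.2 defines its baseline value. SAP 2.5 calls the p-values for the key secondary endpoints descriptive.

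Part of SAP 2.5.2 is redacted just before the WI-VAS sentence, and the weighting equation is not readable. Hidden text could name a covariate. The protocol's model sentence is not redacted and names none.

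**The concern.** A change-score analysis without the baseline value fixes the slope of follow-up on baseline at 1. Putting the baseline in as a covariate lets the data estimate that slope. With 1:1 allocation this cannot increase the large-sample variance of the treatment difference, and it reduces it unless the true slope, within arm and stratum, is 1. It also adjusts for chance imbalance in baseline WI-VAS. The planned model handles baseline severity only through a two-level cut of a different instrument.

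What is at stake is the precision of one secondary endpoint. Because the p-values are descriptive, a reader will lean on the confidence interval, and SAP 3.4.3 does not readably tie that interval to the ANOVA. If the interval is an unadjusted Wald interval, the covariate would sharpen the test but leave the reported interval as it was.

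**Working it through.** **The plan's own figures.** There is no SD, power or sample size for WI-VAS to reproduce. The stated 200 subjects and 90% power concern the primary responder rate. Both assumed rates are redacted, and the figure does not bear on this point.

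**Inputs from the documents.** 200 subjects, 1:1; four strata cells (two WI-NRS bands by two age bands); entry at weekly WI-NRS of 7 or more.

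**Assumed inputs.**
- Baseline WI-NRS normal (8, 1.2) truncated to 7–10: mean 8.29, SD about 0.765, 38.8% at 8.5 or above, mean 7.78 below the cut and 9.10 above it.
- Baseline WI-VAS SD 1.0, 1.4 or 1.8 cm; correlation with baseline WI-NRS 0.4, 0.6 or 0.8.
- Residual SD of follow-up given baseline: 2.7 cm, with 2.0 and 3.4 as alternatives.
- Slope *b* of follow-up on baseline: 0.1 to 1.0.

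**Step 1: what the stratum already absorbs.** The cut at 8.5 explains 0.388 × 0.612 × (9.10 − 7.78)² / 0.765² ≈ 0.705 of the WI-NRS variance. Within strata, the baseline WI-VAS variance is V = SD² × (1 − r² × 0.705). In the middle case (SD 1.4, r 0.6), V = 1.96 × (1 − 0.36 × 0.705) = 1.462.

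**Step 2: gain in residual variance.** The change score has residual variance (1 − b)²V + σ² without the covariate and σ² with it. The proportional reduction is (1 − b)²V / [(1 − b)²V + σ²]. In the middle case with σ = 2.7 (σ² = 7.29):
- b = 0.3: 0.49 × 1.462 = 0.716, and 0.716 / 8.006 = 8.9%. This is worth 200 / 0.911 − 200 ≈ 20 subjects.
- b = 0.5: 0.25 × 1.462 = 0.366, and 0.366 / 7.656 = 4.8%. This is worth about 10 subjects.

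**Step 3: cost.** Residual degrees of freedom fall from 195 to 194 (192 to 191 with the interaction). That multiplies the variance by about 1 + 1/193 = 1.005. The t critical value moves only from 1.9722 to 1.9723. The interval ratio is √[(1 − reduction) × 1.005]: 4.3% narrower at b = 0.3, 2.2% narrower at 0.5, and 0.3% wider at 1.0.

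**Results at σ = 2.7.** The variance range covers all nine SD and correlation pairs. The interval range comes from 3,000 simulated 200-subject trials for each of three pairs: (1.0, 0.8), (1.4, 0.6) and (1.8, 0.4).

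| Slope | Variance reduction | Middle case | Model-based 95% CI |
|---|---|---|---|
| 0.1 | 5.7–24.2% | 14.0% | 2.7–12.7% narrower |
| 0.3 | 3.6–16.2% | 8.9% | 1.6–8.2% narrower |
| 0.5 | 1.8–9.0% | 4.8% | 0.7–4.4% narrower |
| 0.7 | 0.7–3.4% | 1.8% | 0.1–1.5% narrower |
| 1.0 | 0% | 0% | 0.3% wider |

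The top of each variance range needs the largest SD and the lowest correlation together. At slope 0.5 the range is 3.3–15.2% with σ = 2.0 and 1.2–5.8% with σ = 3.4. Using the treatment-by-strata interaction with cell-size weights (an assumption, since the SAP's equation cannot be read) changed the gains by no more than 0.1 percentage point. Mean estimates were within 0.02 cm of zero, as expected for unbiased analyses.

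**Step 4: source of the interval.** In the middle case at b = 0.3, the full width of an unadjusted Wald interval is 2 × 1.96 × √[(0.49 × 1.96 + 7.29) × 0.02] = 1.59 cm. From the adjusted model it is 2 × 1.972 × √(7.29 × 1.005 × 0.02) = 1.51 cm.

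**Cross-check in another parameterisation.** Let k be the ratio of baseline to follow-up SD and ρ their correlation. Ignoring strata, the variance ratio is (1 − ρ²) / (1 + k² − 2ρk). With the WI-NRS stratum in the model, k of 0.4–0.7 and ρ of 0.2–0.6 give a variance change from +0.5% to −18%. With k = 1.0 the reduction is 15–37%. The entry floor makes a ratio well below 1 the more plausible case.

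**The case against.** The strongest reply is that this is a preference. A change-score ANOVA on the randomisation strata is a legitimate prespecified choice, it already adjusts coarsely for baseline itch, and the size of the gain is entirely assumed. That is fair, and it is why the point is only one to consider. In the middle case at slope 0.3 the half-width shrinks by about 0.04 cm against an unadjusted interval (half of 1.59 − 1.51), which is 0.4 mm on a 100-mm line. The assumptions also ignore the limits of the 0–10 cm scale.

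The second reply is that the source of the interval may already be defined. SAP 3.4.2 refers to a weighted-average effect from an equation in Section 2.5, and that equation may be the redacted text. This stands as a caveat: the interval source is unstated in what can be read, which is not the same as missing from the plan.

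Third, a WI-VAS model with its own baseline would differ from the WI-NRS change model that it is meant to resemble. That is little cost, because each endpoint can carry its own baseline.

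None of these replies identifies harm from adding the covariate beyond one degree of freedom.

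**Conclusion.** The point holds as a low-priority improvement. No readable model statement includes baseline WI-VAS, and the value is on hand for every subject who has a change score. The planned test is valid. A modest gain is the fair expectation: roughly 5–9% of residual variance in the middle case at slopes 0.5 and 0.3. The gain shrinks to nothing as the slope approaches 1, and it could be much larger if the baseline and follow-up SDs were similar. Every one of these figures depends on SDs, correlations and slopes that the documents do not give. The primary analysis, the sample size and the decision rule are unaffected.

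**What to change.** Before unblinding:

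1. In SAP 2.5.2 and 3.4.3, add continuous baseline WI-VAS (SAP 3.2 definition) as a covariate to the stratified model for change in WI-VAS. Keep the strata and whatever interaction and weighting apply under 3.4.2.
2. State in 3.4.3 that the reported 95% interval for the treatment difference comes from that adjusted model, unless the redacted text already fixes its source.
3. Record the covariate as a departure from protocol 8.8.3.
4. In the same edit, settle a separate mismatch. Protocol 8.8.3 says "Missing data imputation will be limited to the WI-NRS and WI-VAS endpoints", while SAP 2.5.2 says "Missing data imputation will be limited to the WI-NRS endpoint" and SAP 2.7 says "Missing data imputation will only be used for the WI-NRS endpoints". Reconcile these or record the difference. It does not support the covariate point and hardly affects it: if 10% of subjects were imputed from baseline by the protocol 8.2 rule, the middle-case gain would fall by about a tenth.

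The cost is a few lines of text and one degree of freedom, with an interval up to about 0.3% wider if the slope is near 1. No subject is lost, because the change score already requires the baseline value.
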